### **12.3 Study Assessments**

The assessments for this study are listed in Section 14.1

### **12.4 Patient Discontinuation Criteria**

A patient may be withdrawn from the study treatment or the study for any of the following reasons:

- Request of the patient or patient's representative
- AEs or adverse device effects (ADEs) based on the judgment of the Investigator
- The patient has experienced an AE that meets protocol defined stopping criteria (refer to Section 12.6.2)
- The Investigator decides that it is in the patient's best interest
- The patient is noncompliant with the protocol
- Lost to follow-up
- Death

If a subject is withdrawn at any time, the reason(s) will be recorded in the relevant section of the eCRF. Patients who discontinue from study treatment and remain in the study, will continued to be monitored per the Schedule of Assessments until Day 14 and the safety follow-up phase to Day 42.

Patients discontinued due to AEs or ADEs will be monitored until resolution or stability of the event based on the judgment of the investigator.

### **12.5 Study Drug Information and Dosage**

#### **12.5.1 Identification and Description of Investigational Drug**

Opaganib 250 mg capsules contain the milled active opaganib drug substance along with the excipients microcrystalline cellulose, colloidal silicon dioxide and magnesium stearate vegetal and are encapsulated in gelatin, white opaque body and cap, coni-snap capsules.

Opaganib will be supplied in bottles, each bottle containing 28 capsules

Placebo will be supplied in bottles, each bottle containing 28 capsules

Treatments will be blinded

### **12.5.2 Packaging and Labeling**

The study medication will be packaged in bottles and labelled by the Sponsor.

The labels may include:

Protocol number

Subject number

Dispense Date

Name and contact information for the Sponsor

Route of administration: oral or nasogastric tube

Quantity supplied: 28 per bottle

Pharmaceutical dosage form: Capsules 250 mg

Storage conditions: store drug at -20-25°C (68-77°F) with excursions permitted to 30°C (86°F)

CAUTION: New Drug – Limited by Federal Law To Investigational Use

Bottle number

Lot number

### **12.5.3 Storage and Handling of Investigational Drug**

Study drug should be stored at 20-25°C (68-77°F) with excursions permitted to 30°C (86°F).

## **12.6 Study Drug Administration**

Study drug will be administered with food (after a light to moderate meal) and followed by 240 mL (8 fluid ounces) of water. If the patient can only take opaganib through a nasogastric tube, the contents of the capsule will be suspended in 20 cc normal saline solution and pushed through the nasogastric tube and flushed adequately with sterile water. If the patient is being tube-fed, study drug should be administered shortly after (approximately 15-30 minutes) a tube feed.

In cases where patients are discharged prior to completing their 14 days treatment, they will continue to take the study drug at the same dose and schedule as an outpatient and following the same instruction to take each dose after a light to moderate meal.

### **12.6.1 Study Drug Dose Modification Plan for Study Drug Suspected Toxicities**

Study drug may be withheld for suspected toxicities. Once suspected toxicities resolve to baseline an attempt may be made to re-initiate the study drug, in consultation with the Medical Monitor. Should the suspected toxicities re-occur, the study drug should be withdrawn permanently.

### **12.6.2 Criteria for Stopping Study Drug**

At any time during the study, participants will stop of study drug if it is determined that they have experienced any of the following adverse events (refer to section 17.2 Table 4 for Adverse Event Grade Definitions):

- Any neuropsychiatric adverse event of Grade 3 severity
- Hallucinations of any severity (any Grade)
- Nausea of Grade 3 severity
- Vomiting of Grade 3 severity
- Any Grade 3 or higher event or laboratory abnormality deemed possibly, probably, or definitely related to study drug.

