### 7.4.1 Completed Studies

#### 7.4.1.1 Phase 1b Study in patients with advanced solid tumors (Study No. ABC-101)

Twenty-two patients were enrolled, of whom 21 were treated with doses from 250 mg QD through 750 mg BID. All 21 patients were evaluable for pharmacokinetics, pharmacodynamics and safety. Sixteen were evaluable for efficacy per RECIST 1.1 criteria. Patients received treatment continuously in 28 day cycles and treatment was given while fasting. Mean age of patients entered was 58 years. Seventy one percent were male, 67% white. All patients had received prior chemotherapy and approximately half had prior surgery and/or radiotherapy. Patients had a variety of concomitant medical conditions and were receiving a variety of medications in addition to their antitumor therapy.

The administered oral dose of 500 mg Q12 hours was the maximum tolerated dose. There were no deaths reported during the administration of opaganib. There were no discontinuations due to adverse events (AEs), in 250 mg QD and 250 mg bid cohorts. Common adverse events were nausea (12 patients, 57%), fatigue (12 patients, 57%), vomiting (8 patients, 38%) and neuropsychiatric effects (14 patients, 67%) including anxiety, insomnia, agitation and dysarthria. Of these, only fatigue appeared to be dose-related. Nausea and vomiting were common but not dose-limiting and rarely required discontinuation of treatment. Neuropsychiatric effects were seen at all dose levels, though were more common and bothersome at the highest dose level, 750 mg Q12 hours, considered an intolerable dose.

There were no consistent trends toward increases or grade shifts in liver function tests, hematologic parameters, or other biochemical parameters except for creatinine and lymphocytes. No patient developed clinically significant ECG abnormalities on study. There were no treatment group differences noted for the changes from baseline of QTcF. For more detailed data refer to Investigator Brochure.

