#### **7.4.1.2 Phase 1b Study in patients with advanced multiple myeloma (Study No. ABC-103)**

Thirteen patients received study drug: 3 at 250 mg Q12 hours, 4 at 500 mg Q12 hours and 6 at 750 mg Q12 hours. Median age of patients was 69 years (range 57-89), 7 were males, 7 were white and 6 black. All patients had received multiple courses of therapy with a median of 7 prior lines of treatment (range 3-13) excluding stem cell transplantation. Eight patients had autologous hematopoietic stem cell transplantation.

The administered oral dose of 500 mg Q12 hours was the maximum tolerated dose. There were no deaths reported during the administration of opaganib. Common adverse events included dyspepsia, nausea and vomiting. Eight patients experienced neuropsychiatric effects including altered mental state, confusion, dizziness, hallucinations and insomnia. All patients experiencing neuropsychiatric effects were receiving concomitant narcotic analgesics and several patients were also receiving other psychotropic medications. In several patients, after adjustment of the narcotic analgesic dosing regimen, the symptoms subsided, with maintenance or improvement of pain control. For more detailed data refer to Investigator Brochure.

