### 17.1 Assessment of Casual Relationship

The following categories and definitions for assessing the causal relationship of an event to the investigational product(s) are provided as a guide to be used for evaluating adverse events reported in

this study to determine “suspected adverse reactions” that require expedited reported to regulatory agencies if they are unexpected. In addition to the assessment below, the aggregate number of occurrences will be considered to decide whether the event is a reportable event and requires an IND safety report.

*Table 3. Relationship of Study Medication to Adverse Events*

Unrelated	
The study drug almost certainly (or certainly) did not cause the event. Guidelines:
 
 
There is no reasonable temporal relationship of the event to the administration of drug;
 
The pattern is inconsistent with that known for the drug; and/or
 
There is another obvious etiology.
 

Probably not related	
It is more likely that the event is due to another etiology than due to the study drug. Guidelines:
 
 
There is no reasonable temporal relationship of the event to the administration of drug;
 
The pattern is inconsistent with that known for the drug; and/or
 
There is another more likely etiology.
 

Possibly related	
It is approximately equally likely that the event is due to the study drug as it is due to another etiology. Guidelines:
 
 
There is a reasonable temporal relationship of the event to the study drug;
 
The drug seems as likely as other etiologies to have caused the effect
 

Probably related	
It is more likely that the event is due to the study drug than due to another etiology. Guidelines:
 
 
There is a reasonable temporal relationship of the event to the study drug;
 
The event may be consistent with a known pattern of drug (or drug class) effects;
 
The drug seems more likely than other etiologies to cause the effect;
 
The adverse event diminished upon cessation of study drug exposure or reduction in dose; and/or
 
The adverse event worsened or recurred upon unintentional re-exposure to the study drug (Intentional rechallenge for the purpose of assigning causality should not be performed.)
 

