## 17.2 Adverse Event Grading

Adverse events will be graded according to the revised NCI Common Terminology Criteria for Adverse Events (NCI-CTCAE version 5.0).

If an AE is not listed in the NCI-CTCAE v.5.0, then the Physician will use the terms: mild, moderate, severe, life-threatening, or death to describe the maximum intensity of the AE. For purposes of consistency, these intensity grades are defined as follows:

*Table 4: Adverse Event Grade Definitions*

GRADE		
1	Mild	Mild; asymptomatic or mild symptoms; clinical or diagnostic observations only; intervention not indicated.
2	Moderate	Moderate; minimal, local or noninvasive intervention indicated; limiting age-appropriate instrumental ADL
3	Severe	Severe or medically significant but not immediately life-threatening; hospitalization or prolongation of hospitalization indicated; disabling; limiting self-care ADL
4	Life-threatening	Life-threatening consequences; urgent intervention indicated
5	Fatal	Death related to AE

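### The mandatory stopping rule for neuropsychiatric events names Grade 3 only, so a Grade 4 event judged not related to study drug meets no stopping criterion

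*Protocol*

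**What the plan says.** Section 12.6.2 and the synopsis entry on stopping rules carry the same five criteria, and both are mandatory: a participant who has had one of the listed events will stop study drug.

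- Neuropsychiatric: "Any neuropsychiatric adverse event of Grade 3 severity". No causality condition.
- Hallucinations: any grade, no causality condition.
- Nausea and vomiting: one bullet each, worded at Grade 3 like the neuropsychiatric one.
- All other events and laboratory findings: "Any Grade 3 or higher event or laboratory abnormality deemed possibly, probably, or definitely related to study drug".

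Section 17.2, Table 4, to which section 12.6.2 refers, defines Grade 3 as severe but not immediately life-threatening. Grade 4 is a separate grade: "Life-threatening consequences; urgent intervention indicated". Section 17.1, Table 3, has five causality categories. Two of them lie below possibly related: unrelated, and probably not related, the latter defined as "It is more likely that the event is due to another etiology than due to the study drug".

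**The concern.** A stopping threshold should not release a patient because the event is worse. Here the neuropsychiatric bullet fixes a single grade, while the last bullet fixes a grade and everything above it, but only for events attributed to the drug. The list states a range where it means one: any grade for hallucinations, and Grade 3 or higher in the last bullet. A site that applies the text as written therefore has grounds to read the neuropsychiatric bullet as Grade 3 alone.

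At stake is whether stopping is required or left to judgement for a life-threatening neuropsychiatric event. The bullet omits causality, so the protocol evidently wants these events to stop treatment without an attribution decision. At Grade 4 the wording brings that decision back. The decision can go against relatedness. In the myeloma study (section 7.4.1.2), "All patients experiencing neuropsychiatric effects were receiving concomitant narcotic analgesics", and in several of them the symptoms subsided once the analgesic regimen was adjusted. A more likely alternative cause is one of the Table 3 guidelines for probably not related. The patients in this trial are hypoxaemic and severely ill (section 8), so competing explanations will be available.

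**Working it through.** No arithmetic applies. The check runs the five bullets as a rule over event type, grade and causality.

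Inputs: the bullets in section 12.6.2 and the synopsis; the grade definitions in Table 4 (section 17.2); the causality categories in Table 3 (section 17.1).

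1. Grade 3 and Grade 4 do not overlap. Table 4 excludes immediately life-threatening events from Grade 3 and makes them Grade 4. A criterion that names Grade 3 does not include Grade 4 by definition.
2. The last bullet names three of the five causality categories (possibly, probably, definitely). That leaves 5 − 3 = 2 uncovered: unrelated and probably not related.
3. The resulting requirement for each case:

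| Event | Grade | Judged unrelated or probably not related | Judged at least possibly related |
|---|---|---|---|
| Neuropsychiatric, not hallucination | 3 | Stop (neuropsychiatric bullet) | Stop (neuropsychiatric bullet) |
| Neuropsychiatric, not hallucination | 4 | **No mandatory stop** | Stop (last bullet) |
| Hallucination | any | Stop | Stop |

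4. Other sections were checked for a rule that makes stopping mandatory in the open cell. Section 12.4 says that a patient may be withdrawn for an adverse event on the investigator's judgement; where it mentions stopping criteria, it points back to section 12.6.2. Section 12.6.1 says that drug may be withheld for suspected toxicities, which an event judged unrelated arguably is not. Section 16 requires immediate notification of life-threatening serious events, not stopping. None closes the cell.
5. An event first recorded at Grade 3 that later worsens has already met the neuropsychiatric bullet. The open cell therefore concerns events that present at Grade 4.
6. With 'Grade 3 or higher' in the neuropsychiatric bullet, the open cell becomes a mandatory stop. Every other cell in the table stays as it is.

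**The case against.** The strongest reply is that only a very literal reading creates the gap. A grade in a stopping rule is naturally taken as a threshold, and no sensible investigator would stop for a severe event and continue through a life-threatening one. The remaining case is also narrow: the event must present at Grade 4, not be a hallucination, be judged less than possibly related, and meet an investigator who chooses to continue. Section 17.6.3 warns that the drug may cause neuropsychiatric toxicity, which pushes attribution towards related. Life-threatening events go to the sponsor and Medical Monitor at once (section 16), and the DSMB reviews all adverse events (section 17.6.5). The myeloma experience also transfers only in part: the analgesics listed as allowed in Table 2 are not narcotics, and Appendix 2 prohibits codeine, tramadol and alfentanil, although it does not exclude every opioid.

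All of this stands as a limit on the consequences. It does not make the wording right, because the safeguards offer discretion or notification where the rule is meant to be mandatory.

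A reader might infer three stronger points that the document does not support.

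- *That nausea and vomiting have the same gap.* Their bullets share the wording, but the synopsis names CTCAE v5.0 for these criteria, and section 17.2 brings in the Table 4 terms only as a fallback: "If an AE is not listed in the NCI-CTCAE v.5.0, then the Physician will use the terms". Whether nausea or vomiting has a Grade 4 on the governing scale is not in the document.
- *That the gap is large because the toxicity is common.* The solid tumour study reports "neuropsychiatric effects (14 patients, 67%) including anxiety, insomnia, agitation and dysarthria", but those are events of any grade in oncology patients dosed while fasting, at doses up to one considered intolerable. They say nothing about Grade 4 events judged not related.
- *That section 12.6.1 lets a patient restart after meeting a stopping criterion.* It permits withholding, whereas section 12.6.2 commands stopping. The headings and verbs favour keeping the two apart.

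**Conclusion.** The point holds for the neuropsychiatric bullet, in both section 12.6.2 and the synopsis. As written, a non-hallucination neuropsychiatric event that presents at Grade 4 and is judged unrelated or probably not related triggers no mandatory stop, while the same event at Grade 3 does. The intent is evidently Grade 3 or higher, but neither place says so.

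The practical size is small. One cell of the rule is affected, the protocol gives no frequency for it, and such cases are probably rare. The statistical analysis is untouched. The conclusion rests on reading the bullet literally, and on some neuropsychiatric events being gradable at 4. Table 4 provides for that in events that CTCAE v5.0 does not list; which listed terms reach Grade 4 cannot be read from the document. The change is optional in weight, but it corrects an operative safety threshold and should not be contentious.

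**What to change.** In section 12.6.2 and in the synopsis stopping rules, change the neuropsychiatric bullet to read 'Grade 3 or higher'. Use the same wording in the nausea and vomiting bullets in both places, for consistency only.

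The cost is two added words in three bullets, in two places. Design, data collection and analysis do not change, and the edit can go into the next protocol amendment with a short note to sites.

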## 13 PRIOR AND CONCOMITANT MEDICATIONS

### 13.1.1 Standard of Care Considerations

As the approval and/or guidance for treating COVID-19 are evolving, for the purpose of this protocol, standard of care will be continually redefined by the recommended schemes of treatment according to the severity of the disease, taking into consideration regulatory approvals in one or more regions. These will be documented in a stand-alone document entitled Approved COVID-19 Therapies which will be updated and shared with study personnel regularly.

All other treatments will be considered experimental, pending evaluation and potential future approval. Concomitant use of standard of care, and/or experimental treatments in patients enrolled in this study will be guided by the inclusion/exclusion criteria, prohibited medications and precautionary medications as outlined in the protocol and the study physician's discretion.

### 13.1.2 Allowed Medications

Necessary supportive measures for optimal medical care will be given throughout the study. Additional care may be administered as indicated by the treating physician and patient's medical need, and after discussion with the medical monitor. Supportive medications that are not expected to interact with opaganib and are allowed (Table 2):

*Table 2. Allowed Supportive Medications*

Class/Pharmacological Action	Allowed medication
Analgesia	acetaminophen (paracetamol), naproxen, ibuprofen 
Sleeping medications/anxiolytic	lorazepam
Anti-coagulant medications	heparin, dalteparin, enoxaparin, tinzaparin and fondaparinux, bilvalrudin
Monoclonal antibodies	casirivimab, imdevimab, bamlanivimab, etesevimab
Corticosteroids	dexamethasone 
Other	baricitinib
Antiviral	remdesivir 

Use with caution, opaganib was a borderline inhibitor of MATE-1 in vitro

While interactions with opaganib are theoretically possible, the is low potential and/or an expectation that any clinical sequelae can be managed at the point-of-care.

The drugs listed in the table above are either weak substrates or not considered substrates for enzymes or transporters which are inhibited or induced by opaganib.

Supportive therapies including supplemental oxygen, plasma treatment from convalescent patients and COVID-19 vaccines are allowed and not anticipated to interact with opaganib.

### **13.1.3 Concomitant medications**

Concomitant medications will include all medications that started, or were continuing, during or after administration of the study drug. All concomitant medications and supportive therapy administered starting Day 1 and until the final off-study drug follow-up visit must be recorded on the appropriate eCRF page.

### **13.1.4 Prohibited Medications**

The following medications are prohibited during the study, including the safety follow-up period:

- Medications that are sensitive substrates and narrow therapeutic range drugs which are substrates for CYP1A2, CYP2B6, CYP2C8, CYP2C9, CYP2C19 CYP2D6, CYP3A4, P-gP, BCRP and OATP1B1 should be avoided with opaganib.
- Moderate or strong inhibitors of CYP1A2, CYP3A4, CYP2D6 or P-gP are prohibited as they may increase the systemic exposure (plasma concentrations) of opaganib.
- As azithromycin carries a risk of QTc prolongation and/or torsades de pointe, it should not be co-administered with opaganib.
- Warfarin, apixaban, argatroban and rivaroxaban are prohibited due to drug-drug interaction based on CYP450 metabolism. The washout periods for these drugs:
  - Warfarin ~ 1 week
  - Apixaban- 2.5 days
  - Argatroban- 5 hours
  - Rivaroxaban- 2 days

### **13.1.5 Precautionary Medications**

- Substrates for MATE1 and MATE2-K should be used with caution and monitored for safety due the potential for inhibition of this transporter protein. As the clinical relevance of these in-vitro interactions hasn't been established, these should be decided in discussion with the Medical Monitor on a case-by-case basis.  
Moderate to strong inducers of CYP3A4 and CYP1A2 may influence the exposure of opaganib.

## 14 SCHEDULE OF ASSESSMENTS

### 14.1 Procedures and Assessments

Please see “Schedule of Assessments” for a detailed study schedule (Section 5) presented in tabular form.

#### 14.1.1 Screening (Day -3 to Day 1)

Prior to the initiation of study-specific screening assessments the Investigator or designee must provide the patient(s) a complete explanation of the purpose and evaluations (procedures and assessments) of the study. Subsequently, the patient, or legal representative, must sign and receive a copy of an Informed Consent Form and authorization of use and disclosure of protected health information (PHI) that was approved by the institutional review board (IRB). Once informed consent has been obtained, the eligibility of the patient will be determined, and Screening assessments will be performed. Screening may be performed prior to Baseline (Day -3 to -1) or on the same day as Baseline (Day 1). Patients who have had laboratory or diagnostic tests normally required for screening, but which were performed prior to the ICF being signed, may have those test results used in lieu of the screening tests, if these were part of standard of care, and performed within the same screening window prior to randomization.

- Signed informed consent
- Eligibility determination
- WHO Ordinal Scale for Clinical Improvement level
- Complete medical history (including onset of COVID-19 symptoms, including date of a positive PCR for SARS-CoV-2 prior to screening, where available)
- Concomitant medication assessment
- Baseline review of systems
- Physical examination, specifically assessing for baseline signs of neuropsychiatric (e.g. anxiety, agitation, insomnia), and cardiopulmonary abnormalities (e.g. tachycardia, palpitations, chest pain, syncope)
- Vital signs (temperature, blood pressure, pulse rate, respiratory rate and oxygen saturation by pulse oximeter)
- Height and weight (most recent)
- Oxygen requirement (L/min)- to be repeated prior to first dose as a baseline
- FiO2 estimate
- 12-lead electrocardiogram
- Chest Xray or CT scan (performed up to 7 days of randomization)
- Nasopharyngeal or oropharyngeal swab for SARS-CoV-2 PCR test (collected either at screening or up to 7 days prior to screening)
- Serum chemistry

- CRP, D-Dimer, LDH, ferritin, cardiac troponin (Troponin C, I or T, but must be consistent for each patient throughout the study)
- HbA1c
- CBC with differential
- Urinalysis
- Serum or urine pregnancy test (for women of childbearing potential) within 3 days prior to treatment

